1. INTRODUCTION

The purpose of this reporting and analysis plan (RAP) is to describe the analyses to be included in the Clinical Study Report for Protocol 2015N266248_04.

Revision Chronology:		
Final_V1	08-MAY-2018	Original
Amendment_Final_V1	19-NOV-2018	Amendment 1

2. SUMMARY OF KEY PROTOCOL INFORMATION

2.1. Changes to the Protocol Defined Statistical Analysis Plan

Changes from the originally planned statistical analysis specified in the protocol amendment 04 (Dated: 03/JUL/2017) are outlined in [Table 1](#).

Table 1 Changes to Protocol Defined Analysis Plan

Protocol	Reporting & Analysis Plan	
Statistical Analysis Plan	Statistical Analysis Plan	Rationale for Changes
9.3.3 Adjustment for Multiplicity Adjustment for multiplicity will be applied to maintain an overall type I error rate of 5%. After a preliminary assessment, the primary endpoint will be evaluated to demonstrate the non-inferiority at a one-sided significance level of 2.5% (i.e. two-sided significance level of 5%).	5.5 Multiple Comparisons and Multiplicity Adjustment for multiplicity will be applied to maintain an overall type I error rate of 2.5% (one-sided) . After a preliminary assessment, the primary endpoint will be evaluated to demonstrate the non-inferiority at a one-sided significance level of 2.5%.	An overall type I error rate (α) of 2.5% is a one-sided nature of the non-inferiority test, which is the primary analysis for this study. This can be applicable to the following superiority test to maintain $\alpha=2.5\%$. Practically, this is equivalent to two-sided significance level of 5%.
9.4.1 Primary Efficacy Analysis Analysis of covariance (ANCOVA) will be conducted as sensitivity analysis to MMRM. This model includes treatment group and baseline Hgb.	7.1.6 Sensitivity and Supportive Analyses Analysis of covariance (ANCOVA); it will be conducted as supplementary analysis to MMRM. This model includes treatment group, baseline Hgb, and prior ESA use .	Prior ESA use is considered as important factor impacting Hgb.

2.2. Study Objective(s) and Endpoint(s)

Objectives	Endpoints
Primary Objectives	Primary Endpoints

 To demonstrate non-inferiority of GSK1278863 to epoetin beta pegol based on hemoglobin (Hgb) in ND subjects 	
 Mean Hgb during the primary efficacy evaluation period (Weeks 40 to 52)
Principal Secondary Objectives	Principal Secondary Endpoints

 To demonstrate superiority of GSK1278863 to epoetin beta pegol in terms of achievement/maintenance of target Hgb in ND subjects 	
 Number (%) of subjects with mean Hgb in the target range (11.0-13.0 g/dL) during the primary efficacy evaluation period (Weeks 40 to 52)
Other Secondary Objectives	Other Secondary Endpoints

 To evaluate the appropriateness of the starting dose of GSK1278863 in ND subjects using epoetin beta pegol as control To evaluate the appropriateness of the starting dose of GSK1278863 in PD subjects 	
 Change in Hgb from baseline to Week 4 (Hgb increase rate) Number (%) of subjects by Hgb change category in Hgb from baseline to Week 4

 To evaluate dose adjustments of GSK1278863 in ND subjects using epoetin beta pegol as control To evaluate dose adjustments of GSK1278863 in PD subjects 	
 Distribution of the dose level Duration of treatment interruption due to Hgb >13 g/dL Frequency of dose adjustments

 To evaluate the overall Hgb control by GSK1278863 in ND subjects using epoetin beta pegol as control To evaluate the overall Hgb control by GSK1278863 in PD subjects 	
 Hgb at each assessment time point and change in Hgb from baseline to each assessment time point Number (%) of subjects with Hgb within the target range (11.0-13.0 g/dL) at each assessment time point Proportion (%) of time with Hgb within the target range (11.0-13.0 g/dL) in the primary efficacy evaluation period (Weeks 40 to 52) Time (number of days) to the lower Hgb target (11.0 g/dL) Number (%) of subjects who have an Hgb level of less than 7.5 g/dL Number (%) of subjects who have an Hgb increase of more than 2 g/dL over any 4 weeks before Week 52 Number (%) of subjects who achieve an Hgb level of more than 13.0 g/dL and number of episodes

 To compare the effect of GSK1278863 versus epoetin beta pegol on iron use in ND subjects To evaluate effect of GSK1278863 on iron use in PD subjects 	
 Dose of oral iron in the study period and the primary efficacy evaluation period (Weeks 40 to 52) Number (%) of subjects who use oral iron during the primary efficacy evaluation period (Weeks 40 to 52)

 To compare the effect of GSK1278863 versus epoetin beta pegol on iron metabolism in ND subjects To evaluate the effect of GSK1278863 on iron metabolism in PD subjects 	
 Change in ferritin from baseline Change in transferrin saturation (TSAT) from baseline Changes in hepcidin, serum iron, and total iron binding capacity (TIBC) from baseline

Objectives	Endpoints

 To evaluate the PK of GSK1278863 	
 AUC and Cmax of plasma GSK1278863
Exploratory Objectives	Exploratory Endpoints

 To compare the effect of GSK1278863 versus epoetin beta pegol on progression of CKD in ND subjects 	
 Estimated glomerular filtration rate (eGFR) and change from baseline Serum creatinine and change from baseline Urine creatinine and urine albumin, and changes from baseline Urine albumin/creatinine ratio and change from baseline
Patient Reported Outcome	Patient Reported Outcome Endpoints

 To compare the effect of GSK1278863 versus epoetin beta pegol on health-related QoL (HR-QoL) in ND subjects To evaluate the effect of GSK1278863 on HR-QoL in PD subjects 	
SF-36
 
 Changes in SF-36 HR-QoL scores (PCS, MCS, and 8 subscales) from baseline 
EuroQol Health Utility Index (EQ-5D-5L)
 
 Change in EQ-5D-5L score from baseline Change in EQ-5D-5L Visual Analog Scale (VAS) from baseline
Safety Objectives	Safety Endpoints

 To evaluate the safety and tolerability of GSK1278863 in ND and PD subjects 	
 Incidence and severity of AEs and SAEs, including AEs of special interest Reasons for discontinuation of study medication Laboratory tests, ECG, vital signs, and ophthalmology assessments

2.3. Study Design

Overview of Study Design and Key Features	
Screening phase (4 weeks)	Treatment phase (52 weeks) Primary efficacy evaluation period
Follow-up phase (4 weeks)	
Cohort 1 Non-dialysis (ND) subjects	
GSK1278863 group
 
Epoetin beta pegol group

Cohort 2 Peritoneal dialysis (PD) subjects	GSK1278863 group
Cohort 3 Non-dialysis (ND) subjects	
GSK1278863 group
 
Epoetin beta pegol group

Week -4 Week 52	Day 1 Week 56
Week 40	
Design Features	
 • This is a Phase III, open-label, active-controlled, parallel-group, multi-center study to compare the efficacy (verification of noninferiority) and safety of GSK1278863 administered for 52 weeks versus epoetin beta pegol in approximately 286 Japanese ND subjects with renal anemia. • This study also includes an open-label, uncontrolled part to evaluate the efficacy and safety of GSK1278863 in approximately 50 Japanese PD subjects. • Cohort 1 (ND subjects) and Cohort 2 (PD subjects) were set for target population of this study when the study was planned. • Cohort 3 is newly added in amendment (Amendment No. 3). ND subjects will be randomized not to Cohort 1 but to Cohort 3 after amendment No.3.
Dosing	GSK1278863 Starting Dose

Overview of Study Design and Key Features	
	
(Cohort 1)
 
 • Both ESA non-users and users will start oral treatment with GSK1278863 at the starting dose of 4 mg once daily (Day 1) and remain on the same regimen until the day of Week 4. 
(Cohort 3)
 
 • ESA non-users 
 ○ Baseline Hgb \geq 8.0 g/dL and $<$9.0 g/dL: the subjects will start oral treatment with GSK1278863 at the starting dose of 4 mg once daily (Day 1) and remain on the same regimen until the day of Week 4*. ○ Baseline Hgb \geq 9.0 g/dL and $<$11.0 g/dL: the subjects will start oral treatment with GSK1278863 at the starting dose of 2 mg once daily (Day 1) and remain on the same regimen until the day of Week 4*. • ESA users will start oral treatment with GSK1278863 at the starting dose of 4 mg once daily (Day 1) and remain on the same regimen until the day of Week 4*. 
*: The HemoCue Hgb value will be measured for safety confirmation at Week 2 in ND subjects. When Hgb $>$ 1.0 g/dL increase over 2 weeks, the dose of GSK1278863 is decreased to the next lower dose.
 
(Cohort 2)
 
 • ESA non-users will start oral treatment with GSK1278863 at the starting dose of 4 mg once daily (Day 1) and remain on the same regimen until the day of Week 4. • ESA users will start oral treatment with GSK1278863 at the starting dose of 4 mg once daily (Day 1) and remain on the same regimen until the day of Week 4. 
ESA users should skip ESA on Day 1 when treatment with GSK1278863 is started.
 
Maintenance Dose
 
 • From Weeks 4 to 52, interruption of treatment or dose adjustments will be made within the maintenance dose range of 1-24 mg (Table 6 in the protocol) according to the dose adjustment algorithm (Table 7 in the protocol) to achieve and/or maintain Hgb within the target range (11.0-13.0 g/dL) based on the HemoCue Hgb value measured every 4 weeks. Dose changes will be made every 4 weeks. 
Epoetin Beta Pegol Starting Dose for ESA Non-users
 
 • ESA non-users will start subcutaneous treatment with epoetin beta pegol at a dose of 25 μg once every 2 weeks (Day 1). Dose adjustments will be made within the initial dose range of 25-150 μg (Table 8 in the protocol) according to the dose adjustment criteria (Table 9 in the protocol) to increase Hgb to 11.0 g/dL (lower limit of the target) or more based on the HemoCue Hgb value measured every 4 weeks. Dose changes will be made every 4 weeks. 
Dose Conversion for ESA Users


Overview of Study Design and Key Features	
	
 For ESA users, prior ESA will be replaced with epoetin beta pegol at the equivalent dose once every 4 weeks (Day 1). At Week 2, HemoCue Hgb value will be measured for subjects' safety confirmation. If the measurement shows an Hgb increase of >1.0 g/dL over 2 weeks, the dose of GSK1278863 will be reduced by one step (or treatment interrupted) at Week 4 (Cohort 3 only). 
Maintenance Dose
 
 Epoetin beta pegol will be administered once every 4 weeks from dosing interval change (once every 4 weeks) with Hgb \geq11.0 g/dL to Week 52 in ESA non-users and from Weeks 4 to 52 in ESA users Further details of dosing are provided in the protocol Section 6.4.
Time & Events	
 Refer to Appendix 2: Schedule of Activities
Treatment Assignment	
 The randomization schedule will be generated by GlaxoSmithKline (GSK) using the randomization system (Randall NG). In Cohort 1 and Cohort 3 (ND subjects), subjects will be stratified by the current ESA therapy (ESA non-user or ESA user) and the Hgb level on Day 1 and randomized in a 1:1 ratio to one of the two treatment groups according to the randomization schedule. In Cohort 2 (PD subjects), all eligible subjects will start treatment with GSK1278863 on Day 1.
Interim Analysis	
 No interim analysis is planned.

2.4. Statistical Hypotheses / Statistical Analyses

The primary objective of the study is to demonstrate the non-inferiority of GSK1278863 to epoetin beta pegol based on mean Hgb during the primary efficacy evaluation period (Weeks 40 to 52) in ND subjects, including Cohort 1 subjects (only ESA users) and Cohort 3 subjects (both ESA users and ESA non-users).

As a preliminary assessment, it will be confirmed whether the mean Hgb during the primary efficacy evaluation period in GSK1278863 group would be in the target range (11.0-13.0 g/dL) at first. And then the following non-inferiority statistical hypotheses are to be tested at a one-sided significance level of 2.5% (i.e. two-sided significance level of 5%):

- H_0 : Treatment difference (daprodustat – epoetin beta pegol) in mean Hgb during the primary efficacy evaluation period is -1.0 g/dL or less.
- H_1 : Treatment difference (daprodustat – epoetin beta pegol) in mean Hgb during the primary efficacy evaluation period is greater than -1.0 g/dL.

Only when the primary endpoint achieves non-inferiority, statistical testing will progress to the principal secondary endpoint with a focus on superiority according to the step-

down procedure. More specifically, the superiority of GSK1278863 to epoetin beta pegol in terms of target Hgb control in ND subjects, including Cohort 1 subjects (only ESA users) and Cohort 3 subjects (both ESA users and ESA non-users), is to be demonstrated at a one-sided significance level of 2.5% by testing the following statistical hypotheses:

- H_0 : The proportion of subjects whose mean Hgb during the primary efficacy evaluation period is within the target range (11.0-13.0 g/dL) is equal or less in GSK1278863 than epoetin beta pegol.
- H_1 : The proportion of subjects whose mean Hgb during the primary efficacy evaluation period is within the target range (11.0-13.0 g/dL) is greater in GSK1278863 than epoetin beta pegol.

No hypothesis will be tested in PD subjects (Cohort 2).

3. PLANNED ANALYSES

3.1. Interim Analyses

No interim analysis is planned.

3.2. Final Analyses

The final planned primary analyses will be performed after the completion of the following sequential steps:

1. The study has completed with the last subject's last study visit.
2. All required database cleaning activities have been completed and final database release (DBR) and database freeze (DBF) has been declared by Data Management.
3. Randomization codes have been distributed according to RandAll NG procedures.

4. ANALYSIS POPULATIONS

Population	Definition / Criteria	Analyses Evaluated
All Screening	
 Consists of all subjects who are given subject number and whose data are collected, including demographics at screening 	
 Study Population
Enrolled	
 Consists of subjects in All Screening except for screen failures (who never passed screening even if rescreened). 	
 Study Population (some displays for EudraCT)
Randomized	
 Consists of all subjects who are given randomization number regardless of whether they actually receive study treatment. 	
 Study Population
Safety	
 Consists of all subjects who receive at least one dose of study treatment. Subjects will be analyzed according to the treatment received.^[1] This population will be used for safety analyses. 	
 Study Population Safety
Efficacy Non-dialysis (Efficacy ND)	
 Consists of Cohort 1 subjects (both ESA users and ESA non-users) and Cohort 3 subjects (both ESA users and ESA non-users) who are given randomization number with Hgb measurement at both baseline and at least one scheduled visits following the baseline. Subjects will be analyzed according to randomized treatment. 	
 Study Population Efficacy
Efficacy Peritoneal Dialysis (Efficacy PD)	
 Consists of Cohort 2 subjects who are given randomization number with Hgb measurement at both baseline and at least one scheduled visits following the baseline. 	
 Study Population Efficacy
Intent-To-Treat (ITT)	
 Consists of Cohort 1 subjects (only ESA users) and Cohort 3 subjects (both ESA users and ESA non-users) who are given randomization number with Hgb measurement at both baseline and at least one scheduled visits following the baseline. 	
 Study Population Efficacy

[figure not shown]
Population	Definition / Criteria	Analyses Evaluated
	
 Subjects will be analyzed according to randomized treatment. This population will be the primary population for an assessment of non-inferiority. 	
modified ITT (mITT)	
 Consist of all ITT subjects who have at least one Hgb measurement during the efficacy evaluation period. Subjects will be analyzed according to randomized treatment. This population will be the primary population for an assessment of superiority. 	
 Study Population Efficacy
Per-Protocol (PP)	
 Consists of all mITT subjects who are not major protocol violators. This population will be used for efficacy sensitivity analyses. Protocol deviations that would exclude subjects from the PP population are defined in Section 4.1(Protocol Deviations) and Appendix 1: Protocol Deviation Management and Definitions for Per Protocol Population. 	
 Efficacy
Pharmacokinetic (PK)	
 Consists of all GSK1278863-treated subjects from whom PK samples are collected and analyzed. 	
 PK

NOTES :

- Basically, enrolled population will be the same as randomized population because a subject is going to be given randomized number as soon as passed screening.
- Refer to [Appendix 10](#): List of Data Displays which details the population used for each display.
- Refer to [15.6.2](#) for handling rescreened subjects.

[1]: Only subjects receiving incorrect randomized treatment for the duration of their study participation will be analyzed according to the treatment received. Otherwise, subjects will be analyzed according to the treatment to which they were randomized.

Figure 1 Analysis Populations

NOTES :

- [1]: Subjects who never passed screening even if rescreened
- [2]: Subjects who are not given randomization number
- [3]: Subjects who never receive study treatment
- [4]: Subjects who do not have Hgb measurement at both baseline and at least one scheduled visits following the baseline
- [5]: ESA non-users in Cohort 1 subjects
- [6]: Subjects who have no Hgb measurement during the efficacy evaluation period
- [7]: Subjects who are major protocol violators (See Section 4.1 and [Appendix 1](#))

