7.2.2. Summary Measure

Number (%) of Subjects with Mean Hgb in Target Range during the Primary Efficacy Evaluation Period

The number and percentage of responders, who are subjects with observed mean Hgb within the target range during the primary efficacy evaluation period, and non-responders will be summarized. Odds ratio will be estimated by using a logistic regression and provided along with its 95% CI and superiority one-sided p-value. Analysis will be repeated by the ITT, PP, and Efficacy ND populations in the same manner. The subgroup analysis based on the mITT population will be also produced using tables and a forest plot. For the Efficacy PD population, the summary of the number and percentage of responders and non-responders will be produced and the summary by prior ESA use and baseline Hgb will be created.

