7.2.4. Strategy for Intercurrent (Post-Randomization) Events

Intercurrent events	Strategy
Study withdrawal	The occurrence of the event is taken to be a component of response to treatment. If a subject has no available Hgb data during Week 40 to 52 due to early withdrawal, the subject is deemed as a non-responder. If a subject has at least one available Hgb data during Week 40 to 52, a response to treatment will be defined by whether the mean Hgb during Week 40 to 52 using observed Hgb values within target range.
Prohibited medications (except for commercial ESA medications)	Basically, the occurrence of the event is taken to be irrelevant. Subjects with long-term use of prohibited medications will be excluded from PP population.
Blood transfusion and/or commercial ESA medication	The occurrence of the event is taken to be irrelevant.
Intermittent missing	The occurrence of the event is taken to be irrelevant.

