- The number and percentage of subjects with observed mean Hgb during the primary efficacy evaluation period within the target range (11.0-13.0 g/dL) will be presented by treatment group. If available, the odds ratio (daprodustat/epoetin beta pegol), the associate 95% CI, and a superiority one-sided p-value will also be provided, otherwise 'NC'(not calculated) will be provided for odds ratios and the associated statistics.
- Superiority will be established if the lower limit of the 95% CI for the odds ratio is greater than 1.0 (i.e. a p-value is smaller than 0.025).

Subgroup Analyses

- The subgroup analyses will be based on the mITT population for all subgroup specified in Section 5.4.2 and the Efficacy PD population for baseline Hgb.
- The statistical analysis method uses the same logistic model, unless the logistic model is not applicable due to all responders or all non-responders.
- Graphical summaries for odd ratios and the associated 95% CIs will be produced using a forest plot for the mITT population. If the logistic model is not applicable, 'NC'(not calculated) label will be provided.

Sensitivity and Supplementary Analyses

- The mITT Population will be used for this logistic analysis, and the supplementary analysis using same logistic model will be repeated in the ITT and PP Population to evaluate the robustness of the conclusion. In the ITT population, subjects who have no available Hgb after Week 40 will be considered as non-responder.
- The logistic regression will be performed by a set of pre-specified subgroups (Section 5.4.2). These subgroup analyses are considered exploratory to assess for consistency with the overall results.

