15.3.1. Definitions of Assessment Windows for Analyses

Analysis Time Point	Definitions
Screening ^[1]	Data collected in Screening visit If multiple records are present, the latest record will be used for analysis.
Day 1 ^[1]	Data collected in Day 1 visit If multiple records are present, the latest record will be used for analysis.
Week 2	Data collected in Week 2 visit ^[2]
Week 4	Data collected in Week 4 visit
Week 8	Data collected in Week 8 visit
Week 12	Data collected in Week 12 visit
Week 16	Data collected in Week 16 visit
Week 20	Data collected in Week 20 visit
Week 24	Data collected in Week 24 visit
Week 28	Data collected in Week 28 visit
Week 32	Data collected in Week 32 visit
Week 36	Data collected in Week 36 visit
Week 40	Data collected in Week 40 visit
Week 44	Data collected in Week 44 visit
Week 48	Data collected in Week 48 visit
Week 52	Data collected in Week 52 visit
Follow-up	Data collected in Follow-up visit

Note:

Any unscheduled visit will not be slotted to a particular time point.

[1] For rescreened subjects, data collected in screening-pass visit (i.e. screening and day 1 visit where the subject has passed a screening test) will be used for analysis. They may have multiple records at Screening and/or Day 1 visit, which associates with a screening pass visit and screening failure visit(s) (see Section [15.6.1](#) and Section [15.6.2](#))

[2] Only ND subjects randomized to Cohort 3

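### Randomized non-dialysis subjects with no scheduled post-baseline Hgb fall outside every responder population, so the plan's non-responder rule cannot reach them even in the ITT repeat

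*SAP*

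**What the plan says.** **Populations (SAP Section 4).** ITT takes Cohort 1 ESA users and all Cohort 3 subjects "who are given randomization number with Hgb measurement at both baseline and at least one scheduled visits following the baseline". Efficacy ND adds the Cohort 1 ESA non-users under the same condition. A note to Figure 1 confirms who is removed at that step: "Subjects who do not have Hgb measurement at both baseline and at least one scheduled visits following the baseline". The mITT definition is "Consist of all ITT subjects who have at least one Hgb measurement during the efficacy evaluation period", and the PP definition is "Consists of all mITT subjects who are not major protocol violators". The Randomized population is used for study-population displays only.

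**Responder analysis (Sections 7.2.1 to 7.2.5.1).** The confirmatory superiority test is on mITT. For the other sets, 7.2.2 says: "Analysis will be repeated by the ITT, PP, and Efficacy ND populations in the same manner". Section 7.2.5.1 says the same logistic model "will be repeated in the ITT and PP Population to evaluate the robustness of the conclusion", and that ITT subjects with no Hgb from Week 40 on count as non-responders.

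**Withdrawal (Section 7.2.4).** Withdrawal is a component of the response: "If a subject has no available Hgb data during Week 40 to 52 due to early withdrawal, the subject is deemed as a non-responder".

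**Visits (Section 15.3.1).** The Week 2 analysis time point carries the restriction "Only ND subjects randomized to Cohort 3".

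**The concern.** The post-baseline condition does no harm to the primary MMRM, to which a subject with no post-baseline value contributes nothing. For a responder endpoint with a composite rule for withdrawal it matters, because there a subject with no later data does have a defined outcome: non-response. The population definition removes that subject before the rule can act.

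mITT and PP already require a Week 40-52 Hgb, so the non-responder rule has nothing to do in them. ITT and Efficacy ND are the only sets in which it operates, and the ITT repeat is the planned check that the superiority conclusion survives withdrawal. That check still selects on post-randomization data. The trial is open-label and compares a daily tablet with an injection, so very early departure could differ by arm. The stake is the size of a supportive odds ratio.

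**Working it through.** **1. Set check.** By the definitions, PP lies inside mITT, mITT inside ITT, ITT inside Efficacy ND, and Efficacy ND inside the randomized non-dialysis subjects. The comparative responder tables cover mITT, ITT, PP, Efficacy ND and mITT by subgroup (Tables 2.25 to 2.29). Every one of these requires at least one scheduled post-baseline Hgb. A randomized non-dialysis subject without one is in none of them.

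**2. Who is lost depends on what a scheduled visit is.**
- Narrow reading: only the numbered treatment visits count. Section 7.1.6.3 points this way, since it describes ITT subjects without Hgb from Week 4 on as those withdrawn at Week 2. The first qualifying visit is then Week 2 in Cohort 3 and Week 4 in Cohort 1. A subject leaving in Week 3 can be a non-responder in Cohort 3 but is not counted in Cohort 1.
- Wide reading: Section 15.6.3 names follow-up among the scheduled visits, 15.3.1 lists it as an analysis time point, and the schedule in 15.2.1 plans hematology at early withdrawal and at follow-up. A subject who leaves in Week 1 but gives a follow-up sample would then be in ITT as a non-responder. Only subjects with no later scheduled Hgb at all would be lost.

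**3. Illustration of size.** The SAP gives no early-loss count, responder rate or power, so there is no figure of its own to reproduce. Assumptions: 140 randomized per arm, and 100 (daprodustat) vs 84 (epoetin beta pegol) responders. The SAP plans about 286 non-dialysis subjects at 1:1, so 143 per arm is the ceiling; ITT is smaller because Cohort 1 ESA non-users are left out. The calculation is unadjusted, whereas the planned model adjusts for baseline Hgb and prior ESA use.

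Formulas: OR = [r1/(n1 − r1)] / [r2/(n2 − r2)]; SE of ln OR = √[1/r1 + 1/(n1 − r1) + 1/r2 + 1/(n2 − r2)]; z = ln OR / SE, with a one-sided p.

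| Left out (dap. vs epo.) | Rates | OR | One-sided p |
|---|---|---|---|
| none (all randomized) | 100/140 = 71.4% vs 84/140 = 60.0% | (100/40)/(84/56) = 1.67 | 0.022 |
| 5 vs 1 | 100/135 = 74.1% vs 84/139 = 60.4% | (100/35)/(84/55) = 1.87 | 0.008 |
| 1 vs 5 | 100/139 = 71.9% vs 84/135 = 62.2% | (100/39)/(84/51) = 1.56 | 0.044 |
| 2 vs 2 | 100/138 = 72.5% vs 84/138 = 60.9% | (100/38)/(84/54) = 1.69 | 0.021 |

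First row in full: ln 1.667 = 0.511; SE = √(0.0100 + 0.0250 + 0.0119 + 0.0179) = 0.254; z = 2.01.

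**4. Second set of assumptions.** With 143 per arm, one subject is 100/143 = 0.70 percentage points of an arm. Take a control response of 60% to 80% and daprodustat about 11 points higher among subjects with post-baseline Hgb. Counting the left-out subjects as non-responders changes the difference by about −0.1 points at 1 vs 1, −0.5 at 7 vs 7, −1.1 to −1.3 at 3 vs 1, −2.1 to −2.6 at 5 vs 1, and −2.6 to −3.3 at 7 vs 2.

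**The case against.** - **No decision rests on these analyses.** The confirmatory test is on mITT, the ITT and PP repeats are labelled supplementary, and none of the repeats carries alpha. This stands. A reader might infer from p-values moving across 0.025 that the superiority claim is at risk. The documents do not support that: a crossing in a supplementary table has no formal consequence, and the mITT set is the same either way. The much larger removal of subjects, by requiring a Week 40-52 Hgb for mITT, is a separate matter.
- **Not every early leaver is lost.** A reader might infer that all of the earliest withdrawals escape being counted. On the wide reading of scheduled visits, those who give a follow-up sample, and perhaps an early-withdrawal sample, are in ITT as non-responders. This stands as an ambiguity. It narrows the gap without closing it, because subjects with no later scheduled Hgb are lost on either reading.
- **The cohort difference does not by itself bias the arm comparison.** Each cohort is randomized 1:1 and both arms within it share the same first visit. This also stands; the difference is an inconsistency in how one event is scored, and only on the narrow reading.
- **The imbalances are chosen.** A 5 vs 1 split means 3.6% vs 0.7% of an arm lost within two to four weeks, and nothing in the SAP supports that. The table shows what could happen.
- **The exclusions are visible.** Tables 1.1 and 1.12 to 1.14 and Listing 7 let a reader find these subjects. That helps, but it leaves the reader to redo a robustness analysis that the plan could have run.

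**Conclusion.** The point holds as a gap in the supplementary responder analyses. The SAP has a composite rule for withdrawal, and its population definitions stop that rule from reaching randomized subjects with no scheduled post-baseline Hgb, including in the ITT repeat meant to evaluate robustness. The primary MMRM and the confirmatory mITT test are unaffected.

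The number of subjects is unknown and probably small, and the direction of any bias is unknown. Equal loss in both arms has almost no effect. Unequal loss could move the supplementary odds ratio either way: from 1.67 to 1.87 or to 1.56 under the assumed counts of 140 per arm, 100 vs 84 responders and a 5-to-1 imbalance. Those counts are assumptions, and the calculation is unadjusted.

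**What to change.** In Section 7.2.5.1:

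- Run the ITT responder repeat (Table 2.26) in all randomized Cohort 1 ESA users and all randomized Cohort 3 subjects.
- Run the Efficacy ND repeat (Table 2.28) in all randomized non-dialysis subjects.
- In both, score anyone without a Week 40-52 Hgb as a non-responder, whether or not any post-baseline Hgb exists.
- For the baseline covariate, use the Day 1 HemoCue Hgb where the central laboratory value is missing. Section 15.6.3 already allows this, and Day 1 Hgb and ESA use are stratification factors, so the model inputs should be available.
- Keep the present ITT definition for the MMRM, and state in Section 4 whether early-withdrawal and follow-up samples count as scheduled visits.

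The cost is SAP wording and a few added non-responders; no new data are needed. The downside is that response rates become slightly less favourable.
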